10.5.1 Secondary efficacy objective(s)

10.5.1.1 Progression free survival

PFS is defined as the time from the date of first dose of study medication to the date of the first documented progression or death due to any cause occurring in the study. PFS will be assessed based on local investigator's assessment according to RECIST v1.1 (see Appendix 5 for further details).

PFS will be censored if no PFS event is observed before the cut-off date. The censoring date will be the date of last adequate tumor assessment before the cut-off date. If a PFS event is observed after two or more missing or non-adequate tumor assessments, then PFS will be censored at the last adequate tumor assessment. If a PFS event is observed after a single missing or non-adequate tumor assessment, the actual date of event will be used (see Appendix 5). It is not intended to censor patients for new anticancer therapy prior to documented disease progression in the primary analysis.

The Kaplan-Meier estimate of the PFS survival function will be estimated and displayed. The resulting median PFS time will be given for each cohort with 95% confidence intervals, as well as 25th and 75th percentiles will be reported.

10.5.1.2 Progression free survival 2

PFS2 is defined as time from the date of first dose of study medication to the date of first documented progression on next-line therapy or death from any cause.

The first documented progression on next-line treatment is based on investigator assessment of PD (i.e. as captured on the anti-neoplastic therapy after treatment discontinuation eCRF page);

it is not necessary to continue to collect tumor assessments data for subsequent anti-neoplastic therapies for the purpose of PFS2.

PFS2 will be summarized using the Kaplan-Meier method on the mFAS. The resulting median PFS will be given with 95% confidence intervals for each cohort.

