G	Deaths due to reason other than deterioration of 'Study indication'	(1) Date of last adequate assessment	Censored (only TTP and duration of response)

=Definitions can be found in Section 3.2.8

=After the last adequate tumor assessment. "Date of next scheduled assessment" is defined in Section 3.2.8.
=The rare exception to this is if the patient dies no later than the time of the second scheduled assessment as defined in the protocol in which case this is a PFS event at the date of death.

The primary analysis and the sensitivity analyses must be specified in the protocol. Clearly define if and why options (1) are not used for situations C, E and (if applicable) F.

Situations C (C1 and C2): Progression or death after one or more missing assessments: The primary analysis is usually using options (1) for situations C1 and C2, i.e.

- (C1) taking the actual progression or death date, in the case of only one missing assessment.
- (C2) censoring at the date of the last adequate assessment, in the case of two or more consecutive missing assessments.

In the case of two or missing assessments (situation C2), option (3) may be considered jointly with option (1) in situation C1 as sensitivity analysis. A variant of this sensitivity analysis consists of backdating the date of event to the next scheduled assessment as proposed with option (2) in situations C1 and C2.

Amended Protocol Version 06 (Clean)

Situation E: Treatment discontinuation due to 'Disease progression' without documented progression: By default, option (1) is used for situation E as patients without documented PD should be followed for progression after discontinuation of treatment. However, option (2) may be used as sensitivity analysis. If progression is claimed based on clinical deterioration instead of tumor assessment by e.g. CT-scan, option (2) may be used for indications with high early progression rate or difficulties to assess the tumor due to clinical deterioration.

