4.5.1 Calculation of 'time to event' variables

Time to event = end date - start date + 1 (in days)

When no post-baseline tumor assessments are available, the date of randomization/start of treatment will be used as end date (duration = 1 day) when time is to be censored at last tumor assessment, i.e. time to event variables can never be negative.

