enrollment, allowing for the +1 week visit window for tumor assessments. Patients with only non-measurable disease at baseline will be part of the analysis and will be included in the numerator only if they achieve a complete response or have a 'Non-CR/Non-PD' response 23 weeks or more after start of study treatment. CBR will be calculated using the mFAS based on the investigators' tumor assessments.

Duration of response

Duration of response (DOR) only applies to patients whose best overall response is complete response (CR) or partial response (PR) according to RECIST 1.1 based on local investigators review of tumor assessment data. The start date is the date of first documented response of CR or PR (i.e., the start date of response, not the date when response was confirmed), and the end date is defined as the date of the first documented progression or death due to underlying cancer. Patients continuing without progression or death due to underlying cancer will be censored at the date of their last adequate tumor assessment using the censoring rule described for PFS analysis (options A(1), C2(1), D(1), E(1), F(1-3) and G(1) from Table 3-2 in Appendix 5 of the study protocol).

Overall Survival

OS is defined as the time from date of start treatment to date of death due to any cause. If a patient is not known to have died, then OS will be censored at the date of last known date patient alive.

PFS after next-line of treatment (PFS2)

PFS2 is defined as time from date of start of treatment to the first documented disease progression (clinical or radiologic) on next-line therapy or death from any cause, whichever occurs first. The first documented progression on next-line treatment will be based on investigator assessment of PD (i.e. as captured on the anti-neoplastic therapy after treatment discontinuation CRF page).

1. Next-line therapy is defined as the first new (systemic) anti-neoplastic therapy initiated after discontinuation of study treatment regardless of EoT reason. Drugs given as part of the same regimen should be grouped as one line (i.e. part of the next-line therapy). In addition, continuation of the study treatment after the initial radiologic disease progression will not be considered as next-line therapy.
2. PFS2 will be censored if no PFS2 event (progression or death) is observed during next-line therapy before the analysis cut-off date; the censoring date will be the last contact date.

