3. However, in case a second new anti-neoplastic therapy is introduced without prior PFS2 event, then PFS2 will be censored at the end date of the first new anti-neoplastic therapy (i.e. next line therapy).
4. PFS2 will be censored at last contact date if a patient is still ongoing on study treatment irrespective of the disease progression status or second progression while being on study treatment, or patient has discontinued study treatment but has not started next-line therapy and is still alive.

5. Any death prior to initiation of next-line therapy will be considered as an event for PFS2.
6. PFS and PFS2 may be identical if a patient did not experience an event (i.e. progression) prior to initiation of next-line therapy, and adequate tumor assessments continue until RECIST 1.1-documented disease progression after initiation of next-line therapy.

Extension Phase Clinical Benefit

The secondary objective related to the Extension Phase of the study is to evaluate clinical benefit as assessed by the Investigator. Proportion of patients with clinical benefit is defined by the number of patients with clinical benefit as assessed by investigator during Extension Phase (begins after the end of the Core Phase) divided by the number of patients in Extension Phase (Safety set in Extension Phase).

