New anticancer therapy given prior to protocol defined progression	Ignore the new anticancer therapy and follow situations above	As per above situations
Death before first PD assessment	Date of death	Progressed

ORR

Patients with unknown or missing best overall response (BOR) will be counted as failures. If there is no baseline tumor assessment, all post-baseline overall lesion responses are expected to be 'Unknown'. If no valid post-baseline tumor assessments are available, the best overall response must be "Unknown" unless progression is reported. For the computation of ORR, these patients will be included in the mFAS and will be counted as 'failures'.

PFS 2

For PFS2, refer to [Table 2-6](#) for censoring and event date options and outcomes.

Table 2-6 Outcome and event/censor dates for PFS2 analysis

Situation	Event/Censoring Date	Outcome
No baseline assessment	Date of start of treatment	Censored
Progression or death during the next-line therapy	Date of progression (or death)	Event
Death prior to initiation of next-line therapy	Date of death	Event
No progression (or death) during the next-line therapy and no second new anti-neoplastic therapy is initiated	Last contact date	Censored
No progression (or death) during the next-line anticancer therapy and a second new anti-neoplastic therapy is initiated	End date of the next-line therapy	Censored
No next-line therapy initiated with patient known to be alive	Last contact date	Censored

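### SAP Table 2-6 censors PFS2 on Day 1 when the baseline tumor assessment is missing, in conflict with the SAP's PFS2 definition and with the table's other rows

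*SAP*

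**What the plan says.** SAP Amendment 4, section 2.7.1, defines PFS2 as the time from start of treatment to the "first documented disease progression (clinical or radiologic) on next-line therapy or death from any cause, whichever occurs first". The progression date is the investigator's, "as captured on the anti-neoplastic therapy after treatment discontinuation CRF page". Six numbered items follow. Item 5 states: "Any death prior to initiation of next-line therapy will be considered as an event for PFS2". Items 2 and 4 censor event-free patients at the last contact date. Item 3 censors at the end of next-line therapy if a second new therapy starts without an event. None of the six items makes PFS2 depend on a baseline scan.

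Table 2-6 in section 2.7.3 turns this into six rows. Row 1 is "No baseline assessment", with date "Date of start of treatment" and outcome censored. Rows 2 and 3 make progression or death during next-line therapy, and death before it, events. Rows 4 to 6 cover event-free patients: last contact date in rows 4 and 6, end of next-line therapy in row 5. Row 1 is identical to the first row of the PFS table (Table 2-5). The table does not say which row governs when a patient fits more than one.

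The extension-phase SAP (section 2.1) refers back to Amendment 4 for all main analyses, so Table 2-6 is still in force.

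**The concern.** The row makes sense for PFS. There, only RECIST progression counts as progression (SAP 2.7.1), and without any baseline scan the overall lesion response is unknown at every visit (Protocol Appendix 5, section 2.5). PFS2 is built differently. Its events are a date that the investigator enters on a CRF page, or a death, and neither has to be compared with baseline lesions. A missing baseline scan therefore does not stop a PFS2 event, or PFS2 follow-up, from being observed.

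Read as written, row 1 would give a patient with a recorded death or next-line progression a one-day censored record. Because rows 2 to 6 describe the same patient and no precedence is stated, two programmers could both follow the SAP and derive different PFS2 data. The same death would still count in overall survival, which has no baseline-scan rule, so the two endpoints would disagree about an observed death.

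**Working it through.** The documents give no PFS2 figure to reproduce. The check is a comparison of rules, followed by an illustration of size.

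**Step 1: the rules side by side, for an mFAS patient with no baseline scan.**

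| Patient's course | Row 1 | SAP 2.7.1 | Other row of Table 2-6 |
|---|---|---|---|
| Dies before next-line therapy | Censored, Day 1 | Event (definition, item 5) | Row 3: event at death |
| Progresses or dies during next-line therapy | Censored, Day 1 | Event (definition) | Row 2: event at that date |
| On next-line therapy, no event, no second new therapy | Censored, Day 1 | Last contact (item 2) | Row 4: last contact |
| Second new therapy starts, no prior event | Censored, Day 1 | End of next-line therapy (item 3) | Row 5: same |
| Alive, no next-line therapy | Censored, Day 1 | Last contact (item 4) | Row 6: last contact |

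Row 1 disagrees in every line. Limiting it to event-free patients would remove the conflict in the first two lines but not in the other three.

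**Step 2: such a patient is in the analysis set.** PFS2 is analyzed in the mFAS (SAP 2.7.2). That set requires assigned and received treatment and a confirmed PIK3CA mutation, not a baseline scan (SAP 2.2). The ORR text in SAP 2.7.3 also keeps patients without a baseline assessment in the mFAS, as failures.

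**Step 3: what a Day 1 record does.** Appendix 5, section 4.5.1, counts time as end date minus start date plus 1, so the record lasts 1 day. If no one has an event on Day 1, the patient leaves the risk set before the first event, and the Kaplan-Meier estimate is the same as if the patient had been deleted.

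Example: 111 simulated uncensored patients (exponential, median 12 months, earliest event on day 4), plus one patient without a baseline scan who dies on day 200. The 12-month estimate is:
- patient removed: 55/111 = 0.4955
- patient censored on Day 1: 0.4955
- death counted: 55/112 = 0.4911

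The difference is 0.4955 − 0.4911 = 0.0044.

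**Step 4: effect on a cohort median.** Assumptions, none of them from the documents: k of 112 patients affected with k between 0 and 2, exponential PFS2, and a median of m months in the other patients. With row 1 applied, the expected cohort median is m. With rows 2 to 6 applied, and affected patients at half the median, the survival function for w = k/112 is

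S(t) = (1 − w)·2^(−t/m) + w·2^(−2t/m), solved for S(t) = 0.5.

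| m (months) | Row 1 | Rows 2 to 6, k = 1 | Rows 2 to 6, k = 2 |
|---|---|---|---|
| 12 | 12.0 | 11.92 | 11.85 |
| 18 | 18.0 | 17.88 | 17.77 |

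With k = 0 nothing changes. If the affected patients have the same prognosis as the rest, the median does not move, and the cost is the lost information: 1/112 = 0.9% or 2/112 = 1.8% of patients.

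**The case against.** The strongest defense is that the row has a source. Appendix 5, section 3.2.4, says that PFS2 censoring follows the same principles as PFS, and Table 3-2 of that appendix makes censoring at start of treatment the default when there is no baseline assessment. This explains where the row came from. It does not reconcile the row with the SAP's own definition, item 5, or the other rows.

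Several stronger readings are tempting, and the documents do not support them:

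- *PFS2 never uses study scans.* Item 6 describes patients whose study assessments continue until RECIST progression after next-line therapy has started, so a study scan can date a PFS2 event. It is not required, and deaths never need one.
- *Recorded events will certainly be discarded.* That is the plain reading of row 1, but without a stated precedence a programmer could equally apply rows 2 and 3.
- *Protocol 10.5.1.2 rules the row out.* Its statement that "it is not necessary to continue to collect tumor assessments data for subsequent anti-neoplastic therapies for the purpose of PFS2" concerns scans on later therapies, not a missing baseline scan. That section helps only through its definition, which includes death from any cause.
- *The SAP dropped a protected class of early deaths.* Appendix 5 attaches an exception to the parent rule: "The rare exception to this is if the patient dies no later than the time of the second scheduled assessment". Its wording is absent from Table 2-6, but row 3 covers every death before next-line therapy, which is broader.
- *The row biases PFS2 upward.* Nothing in the documents says how patients without a baseline scan fare. The half-median case above is an illustration only.

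The argument that few patients are affected stands in full. Chest, abdomen and pelvis imaging is mandated at screening (Protocol 7.2.1.1, Table 7-3), and routine scans from the previous 45 days are accepted. Inclusion criterion 8 requires a measurable lesion or a predominantly lytic bone lesion, which is hard to establish without imaging. The affected group may be empty.

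**Conclusion.** The conflict is real and internal to the SAP. Row 1 applies a PFS rule to an endpoint that does not require a baseline study scan. It contradicts the PFS2 definition, item 5 and rows 2 and 3 for patients with an event, and the last-contact-date rule in items 2 and 4 and rows 4 and 6 for patients without one. Since no precedence is stated, the SAP does not fix a single derivation for these patients.

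The impact is very small. With an assumed 0 to 2 affected patients per cohort of 112, the illustration moves the median by 0 to 0.15 months (m = 12) or 0 to 0.23 months (m = 18) if they do half as well as the rest, and not at all if they do equally well. PFS2 is a descriptive secondary endpoint with no hypothesis test, and the primary endpoint is untouched. No direction of bias can be claimed.

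**What to change.** Delete the first row of Table 2-6. Patients without a baseline assessment then follow the remaining rows: event at next-line progression or death, otherwise censored as rows 4 to 6 state. The matching row in Table 2-5 can stay for PFS. The cost is one table row, with no new data. If PFS2 has already been reported, state how many patients row 1 was applied to and, if there are any, re-derive their records.

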3.2.4 PFS2

A recent EMA guidance (EMA 2012) recommends a substitute end point intermediate to PFS and OS called PFS2, a surrogate for OS when OS cannot be measured reliably, which assesses the impact of the experimental therapy on next-line treatment. The main purpose of this endpoint is to assess long term maintenance strategies, particularly of resensitizing agents and where it is necessary to examine the overall "field of influence".

PFS2, which could be termed PFS deferred, PFS delayed, tandem PFS, or PFS version 2.0, is the time from date of randomization/start of treatment to the date of event defined as the first documented progression on next-line treatment or death from any cause. The censoring rules for this endpoint will incorporate the same principles as those considered for PFS in this document, and in addition may involve other considerations which will need to be detailed in the protocol.

Please note that data collection for the PFS2 is limited to the date of progression and not specific read of the tumor assessments.

Page 185

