from day of patient’s informed consent to the day before first administration of study treatment.
- ***on-treatment period:***
from date of first administration of study treatment to 30 days after date of last actual administration of any study treatment (including start and stop date).
- ***post-treatment period:***
starting at day 31 after last administration of study treatment.

Safety summaries (tables, figures) include only data from the on-treatment period with the exception of baseline data which will also be summarized where appropriate (e.g. change from baseline summaries). In addition, a separate summary for death including on treatment and post treatment deaths will be provided. In particular, summary tables for adverse events (AEs) will summarize only on-treatment events, with a start date during the on-treatment period (***treatment-emergent*** AEs).

However, all safety data (including those from the post-treatment period) will be listed and those collected during the pre-treatment and post-treatment period will be flagged.

Windows for multiple assessments

In order to summarize laboratory parameters, vital sign and other data collected over time (including unscheduled visits), the assessments will be time slotted. The following general rule will be applied in creating the assessment windows: If more than one assessment is done within the same time window, the assessment performed closest to the target date will be used. If 2 assessments within a time window are equidistant from the target date, then the earlier of the 2 assessments will be used. If multiple assessments on the same date then the worst case will be used. Data from all assessments (scheduled and unscheduled), including multiple assessments, will be listed.

Time windows for laboratory assessments

Assessment	Target day of assessment	Time Interval
Baseline		\leq Day 1
Cycle 1 Day 8	8	Day 2 to day 11
Cycle 1 Day 15	15	Day 12 to day 21
Cycle 2 Day 1	29	Day 22 to day 42
Cycle 3 Day 1	57	Day 43 to day 63
Cycle 3 Day 15	71	Day 64 to day 77
Cycle 4 Day 1	85	Day 78 to day 98
Cycle k Day 1 ($k \geq 5$)	$d = (k-1) * 28 + 1$	Day $d-14$ to day $d+13$
End of Treatment		Assessment taken at the end of treatment visit

Last contact date

The last contact date will be derived for patients not known to have died at the analysis cut-off using the last complete date among the following:

Table 2-1 Last contact date data sources

Source data	Conditions
Date of Enrollment	No condition

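### SAP PFS2 item 2 and Table 2-6 count a death only before or during next-line therapy, which conflicts with the protocol's and the SAP's own definition of death from any cause

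*SAP*

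**What the plan says.** **Definition.** Protocol 10.5.1.2 runs PFS2 from first dose to "first documented progression on next-line therapy or death from any cause". Protocol Appendix 5, section 3.2.4, uses the same event: "first documented progression on next-line treatment or death from any cause". The opening sentence of the PFS2 paragraph in SAP 2.7.1 (Amendment 4) also has death from any cause, taken with progression as whichever comes first. It counts both clinical and radiologic progression.

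**Censoring.** Appendix 5 says PFS2 censoring follows the principles used for PFS and "may involve other considerations which will need to be detailed in the protocol". The protocol body adds none. The rules are in the SAP:
- Item 2 of SAP 2.7.1: "PFS2 will be censored if no PFS2 event (progression or death) is observed during next-line therapy before the analysis cut-off date", with the last contact date as censoring date.
- Item 3: if a second new therapy starts with no earlier PFS2 event, "PFS2 will be censored at the end date of the first new anti-neoplastic therapy".
- Item 5: a death before next-line therapy starts is an event.
- Table 2-6 in SAP 2.7.3 has two rows in which death is an event: during next-line therapy (row 2) and before it starts (row 3). Row 4, "No progression (or death) during the next-line therapy and no second new anti-neoplastic therapy is initiated", is censored at last contact. Row 5 mirrors item 3. Row 6 covers patients with no next-line therapy and states that they are known to be alive.

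**Last contact date.** SAP 2.1.1: "The last contact date will be derived for patients not known to have died at the analysis cut-off".

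**The concern.** Next-line therapy has an end date. Item 3 and row 5 use it, and protocol 7.2.1.2 collects it. A patient can therefore stop next-line therapy for toxicity, by choice or on completing a course, with no progression recorded, receive no further line, and die later. By the definition that death is a PFS2 event. By item 2 and Table 2-6 it is not, because it came neither before nor during next-line therapy.

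Median PFS2 with a 95% confidence interval is reported for each cohort, and there is no comparator in which the same handling would offset the effect. Protocol 7.1.9 already collects these deaths through survival follow-up every 12 weeks to the end of the Core Phase, so the information is in hand but would not be used.

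**Working it through.** The plan states no sample size, power or event count for PFS2, so there is no figure to reproduce. The check has three steps.

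**1. Apply the rules to one patient (invented days).** Next-line therapy runs from day 240 to day 330, with no progression recorded. The patient is last known alive on day 440 and dies on day 450.

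| Situation | Definition | Table 2-6 read literally |
|---|---|---|
| No second new therapy | Event, day 450 | Row 4: censored, day 440 if the last-alive date is used |
| Second new therapy started | Event, day 450 | Row 5: censored, day 330 |

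In the first situation the censoring date is itself undefined, because SAP 2.1.1 derives a last contact date only for patients not known to have died. Row 4 also lacks row 6's condition that the patient is alive.

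**2. Direction.** The Kaplan-Meier curve is a product of factors (1 − d/n) over event times. Suppose a death at time t is censored at t instead. With one death at t, the factor (1 − 1/n) is replaced by 1 and every other factor is unchanged, so the curve can only stay level or rise. If the censoring date is somewhat before the death, the risk set is one smaller in the gap. That can offset the rise slightly but, as step 3 shows, does not reverse it.

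**3. Size, under assumed inputs.** The documents give no rate for this path. Assumptions:
- exponential times, with median 8 months from first dose to next-line therapy and median 5 months on it;
- a fraction f leave next-line therapy without recorded progression;
- half of those start a second line (censored at the end of next-line therapy under both rules);
- the other half start nothing and die with median 4 months;
- administrative censoring is uniform over 18 to 36 months.

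Median PFS2 in months, simulated with 1,000,000 patients per row (differences from unrounded medians):

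| f | Deaths dropped per 112 | Table 2-6 literal | Deaths counted | Difference |
|---|---|---|---|---|
| 2% | 0.7 | 15.8 | 15.7 | 0.1 |
| 5% | 1.8 | 16.2 | 16.0 | 0.2 |
| 10% | 3.5 | 16.8 | 16.4 | 0.4 |
| 20% | 7.0 | 18.4 | 17.4 | 1.1 |
| 30% | 10.6 | 20.4 | 18.4 | 2.0 |

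Placing last contact up to 12 weeks before death, as the survival follow-up interval would allow, gives differences of 0.1, 0.2, 0.4, 1.0 and 1.9 months.

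**The case against.** **The rule may not censor these deaths at all.** Since last contact date is defined only for patients not known to have died, row 4 may have been meant for living patients, with the headline definition governing any death. That reading is open, so a reader should not infer that the SAP certainly censors them. It does not remove the defect: row 4 does not state the condition that row 6 states, item 2 carries the same restriction, and on this reading the death has no row. The programmer would have to supply a rule.

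**The affected patients need not be those who were failing.** One might infer that the dropped deaths belong to patients taken off next-line therapy because of decline. The documents do not support this. PFS2 progression includes clinical progression per the investigator, and protocol 7.2.1.2 records the reason for stopping and the progression date. A stop for disease-related decline can already be an event. What remains is mainly stops for toxicity, choice or a completed course, and under-recorded progression.

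**Censoring when a second line starts is deliberate.** Item 3 and row 5 agree and are explicit. They also depart from the unrestricted definition, but this is a chosen rule and not an oversight. What stands is that the departure is undeclared: SAP Section 4, on changes to protocol-specified analyses, covers only COVID-19.

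**The consequence is small.** PFS2 has no hypothesis test and no power statement, and OS, which counts every death, is reported beside it. With 112 patients in the 10% scenario, the median's 95% sampling range is about 13.6 to 19.6 months, so a shift of 0.1 to 0.4 months would not be discernible. This is correct and limits the importance of the point. It is not a reason to leave a rule that contradicts its own definition.

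**Conclusion.** The point holds. Item 2 of SAP 2.7.1 and Table 2-6 conflict with the PFS2 definition in protocol 10.5.1.2, in Appendix 5 and in the SAP itself. A death after next-line therapy ends, with no recorded progression and no further therapy, is on the literal text censored at an undefined date, and on the charitable reading is not covered.

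The bias is upward in median PFS2. Its size depends on how many patients follow this path, which the documents do not say. Under the assumptions above it is about 0.1 to 0.4 months for 2 to 10% of patients. The 1 to 2 months at 20 to 30% are upper bounds, and a reader should not take them as the expected overstatement. The primary endpoint, type I error, power and sample size are unaffected.

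**What to change.** In SAP 2.7.1 item 2 and in rows 2 and 4 of Table 2-6:
- **Event, on its date:** progression on next-line therapy, or death from any cause after next-line therapy starts and before any second new anti-neoplastic therapy.
- **Censored at last contact date:** only patients not known to have died, with no progression on next-line therapy and no second new therapy.

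Item 3 and row 5 may stay, but list them in SAP Section 4 as a departure from the protocol definition. A sensitivity analysis treating the start of the second new line as an event is optional; neither document calls for it.

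The cost is a wording change and one derivation. No new data are needed, because survival follow-up already collects the deaths. The downside is that median PFS2 may come out slightly shorter.
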